## Study Protocol

**Background:** Foot drop is a common gait impairment in individuals with stroke. Clinically, ankle-foot orthoses (AFOs) are frequently prescribed to provide ankle stability and support during the swing phase of gait. Previous studies have shown that AFO use can improve gait symmetry, increase walking speed, and reduce oxygen consumption during walking. The ability to walk while performing concurrent tasks is essential for individuals with stroke to function safely in community environments. Functional near-infrared spectroscopy (fNIRS) can be used to measure changes in oxygenated hemoglobin (HbO) concentration in the prefrontal cortex, reflecting cognitive workload during walking tasks. Carbon-fiber AFOs can store and release elastic energy during the gait cycle, assisting push-off and improving walking efficiency. Previous studies have shown that walking with carbon-fiber AFOs can increase walking speed and reduce oxygen consumption. However, whether carbon-fiber AFOs reduce prefrontal cortical workload during dual-task walking in individuals with stroke remains unclear. Therefore, this study **aims** to investigate the effects of carbon-fiber AFOs on dual-task performance and prefrontal cortical activation during dual-task walking in individuals with stroke.

**Design:** A repeated-measures design will be adopted with two AFO conditions (with AFO and without AFO) and three walking task conditions (single-task walking, cognitive dual-task walking, and motor dual-task walking).

**Methodology protocols:** Participants with stroke will complete the Mini-Mental State Examination (MMSE) to confirm cognitive eligibility, provide demographic information, and will sign the informed consent form. Functional near-infrared spectroscopy (fNIRS) sensors will be placed on the participant's forehead and secured using an elastic headband. Inertial sensors will be attached to the dorsum of both feet to record gait performance. An additional inertial sensor will be attached to the center of the tray to assess tray stability. Participants will be instructed to walk at a self-selected comfortable speed along a 13-m walkway under all conditions. Two experimental factors will be examined: AFO condition and dual-task condition. Participants will wear their own athletic shoes during all walking trials.

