### **Statistical Analysis Plan:**

Since it is difficult to directly compare the motor and cognitive dual-task walking conditions, the analysis will be conducted separately for each dual-task condition.

To analyze gait parameters, a repeated-measures ANOVA will be used to examine the effects of task condition and AFO use. In addition, dual-task cost (DTC) will also be calculated for each gait parameter to quantify the relative change in performance during dual-task walking. Hotelling’s  $T^2$  test may be used to compare the dual-task cost of multiple gait variables between walking with and without an AFO. To evaluate secondary task performance, Hotelling’s  $T^2$  test will be used to examine the dual-task cost of correct response rate and reaction time between the AFO and no-AFO conditions. To examine changes in oxyhemoglobin(HbO) concentration in the prefrontal cortex, a repeated-measures ANOVA will be conducted at the subject level to test the effects of task and AFO use. If variability in participants’ mobility function is observed, a linear mixed model will be applied to control for accounting for inter individual difference and to evaluate the effects of task and AFO use at the trial level. All statistical analyses will be performed using IBM SPSS Statistics (version 19.0), and the level of statistical significance will be set at  $p < 0.05$ .

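### Prefrontal activation is judged on HbO alone, with no named test of workload, so a non-neural effect of the AFO on forehead blood flow may create or hide an apparent reduction

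*Combined protocol and SAP*

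**What the plan says.** The Background under Study Protocol presents fNIRS as a way to measure "changes in oxygenated hemoglobin (HbO) concentration in the prefrontal cortex, reflecting cognitive workload during walking tasks". The Statistical Analysis Plan carries this through with one signal: "To examine changes in oxyhemoglobin(HbO) concentration in the prefrontal cortex, a repeated-measures ANOVA will be conducted at the subject level". The factors are task and AFO, analysed separately for the cognitive and the motor dual task. The plan does not say whether the AFO main effect or the task-by-AFO interaction answers the workload question. A mixed model at trial level follows only if mobility function is seen to vary, and its purpose is to allow for differences between people.

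On physical demand, the Background states: "Previous studies have shown that walking with carbon-fiber AFOs can increase walking speed and reduce oxygen consumption". In the methodology paragraph: "Participants will be instructed to walk at a self-selected comfortable speed along a 13-m walkway under all conditions". The fNIRS "sensors will be placed on the participant's forehead and secured using an elastic headband". Gait is measured too: "Inertial sensors will be attached to the dorsum of both feet to record gait performance". The HbO analysis does not use the gait data.

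Neither the protocol nor the SAP describes HbR, short-separation channels or another correction for superficial signal, a recording of heart rate, blood pressure or breathing, or adjustment of HbO for walking speed.

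**The concern.** Light from a forehead sensor crosses the scalp on its way to and from the cortex, so measured HbO mixes cortical response with skin and systemic blood flow. This is a general property of the technique and is not stated in the documents. What the documents do supply is a reason to expect the systemic part to differ between the two conditions compared: by the protocol's own account the device can alter speed and oxygen use, and the design does not hold speed fixed.

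At stake is the study's new claim. The Background treats the speed and oxygen benefits as already shown and the effect on prefrontal workload as the open question. An AFO main effect on HbO could partly restate the known benefit as the new one. It could also miss a real reduction if the systemic shift runs upward.

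**Working it through.** **No figure to reproduce.** The documents give no sample size, effect size, SD or power. The only numerical input is the 0.05 significance level, taken as two-sided because sidedness is not stated.

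**Step 1: what each ANOVA effect contains.** Write the AFO-minus-no-AFO change in HbO as ΔC + ΔS (cortical plus systemic), for single-task and dual-task walking.

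- AFO main effect = average of ΔC over the two tasks + average of ΔS over the two tasks.
- Task-by-AFO interaction = (ΔC dual − ΔC single) + (ΔS dual − ΔS single).

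The main effect carries the whole systemic shift. The interaction is free of it only if ΔS is the same in single- and dual-task walking. The interaction also removes any cortical effect common to both tasks, so it speaks to dual-task workload specifically.

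**Step 2: what a shift could do (illustration).** Take the paired AFO contrast with ΔC = 0 and a downward systemic shift of dz SDs of the paired difference. The test statistic is noncentral t with n − 1 degrees of freedom and noncentrality −dz√n. For n = 20 and dz = 0.5 the noncentrality is −0.5 × √20 = −2.24. Probability of a significantly lower HbO, with every n and dz assumed:

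| n | dz = 0 | 0.2 | 0.5 | 0.8 |
|---|---|---|---|---|
| 12 | 0.025 | 0.092 | 0.353 | 0.714 |
| 20 | 0.025 | 0.133 | 0.564 | 0.924 |
| 30 | 0.025 | 0.184 | 0.754 | 0.988 |

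The argument is symmetric. An upward shift gives the same probabilities of a significantly higher HbO. If a real cortical fall of 0.5 SD met an upward systemic shift of 0.5 SD, the net would be −0.5 + 0.5 = 0. At n = 20 the chance of detecting the fall would then drop from 0.564 to 0.025.

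**Step 3: what speed adjustment could do (illustration).** In a simulation of 3,000 runs per cell there is no neural effect. The systemic shift acts wholly through the within-person speed difference, with an assumed correlation of −0.7 with the HbO difference. The proportion of runs significant in either direction was:

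| n | dz = 0.35, unadjusted | adjusted | dz = 0.70, unadjusted | adjusted |
|---|---|---|---|---|
| 12 | 0.213 | 0.046 | 0.604 | 0.050 |
| 20 | 0.314 | 0.051 | 0.848 | 0.047 |
| 30 | 0.480 | 0.049 | 0.962 | 0.044 |

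Adjustment restores roughly 0.05 because the simulation routes the whole shift through speed. It shows nothing about systemic change unrelated to speed, and it does not test the HbR comparison.

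**Step 4: precision of the interaction.** Assume the four cell means of one 2 × 2 analysis have common variance σ² and common correlation ρ. Each AFO difference then has variance 2σ²(1 − ρ), and the two differences are uncorrelated. Their average (the main effect) has variance σ²(1 − ρ). Their difference (the interaction) has variance 4σ²(1 − ρ). The standard error of the interaction is therefore √4 = 2 times that of the main effect.

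**The case against.** The strongest reply is that the design already contains a control. Single-task walking is recorded with and without the AFO, and a systemic shift common to both tasks falls on the main effect and drops out of the interaction. A reader might infer that the planned HbO data cannot separate cortical from systemic change at all; that goes too far, because this partial control exists. What remains is that the SAP does not name the interaction as the test of workload, and that the cancellation requires a similar shift in both tasks.

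A reader might also infer that the bias favours the AFO. The documents do not support a direction: faster walking and lower oxygen consumption may push systemic signal opposite ways.

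Other replies have some force. Walks of 13 m with rests between trials may keep systemic change small. Speed is measured and analysed as a gait outcome, so a speed difference would at least be visible beside the HbO result. Stroop accuracy, reaction time and fallen blocks give some indirect evidence, though the plan does not use them to interpret HbO. The within-person design and the conditional mixed model help less: both address differences between people, and neither removes a within-person change brought about by the AFO.

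Finally, scalp contamination, the usual opposite movement of HbO and HbR in cortical activation, and the availability of HbR are general knowledge about fNIRS. The documents specify no device or exported signals.

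**Conclusion.** The concern holds as a limit on interpretation. On the text, HbO is the only cortical signal analysed, the effect that tests workload is unnamed, and the protocol itself expects the AFO to change physical demand at uncontrolled speed. An AFO main effect on HbO may therefore be partly non-neural, and may create or conceal an apparent reduction.

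Its size and direction cannot be computed from the documents. The tabulated probabilities show only what assumed shifts would do at assumed sample sizes; a reader should not take them as this trial's false-positive rate. The conclusion rests on two assumptions from outside the documents: that forehead HbO includes superficial and systemic flow, and that this component responds to walking speed or effort. The point does not invalidate the trial, but it bears on what the trial may say about workload and should be settled before results are seen.

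**What to change.** In the Statistical Analysis Plan:

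1. Name the task-by-AFO interaction (dual-task minus single-task HbO, with versus without AFO), separately for the cognitive and motor tasks, as the test of dual-task workload. Note that it cancels a systemic shift only if the shift is similar in single- and dual-task walking.
2. Run the same model on HbR from the same channels and time window as a supporting analysis, and report estimates with confidence intervals for both signals. This assumes the device outputs HbR, as systems that compute HbO normally do; the sponsor should confirm it.
3. Fix the reading rule in advance. Describe an HbO fall as reduced prefrontal activation with support only when HbR moves in the opposite direction, judged by a stated criterion such as a confidence interval lying wholly on that side of zero. Where HbR is flat, inconclusive or moves in parallel, report a haemodynamic difference that may be systemic. A flat or imprecise HbR result must not count as support, because a systemic change may simply lack the opposite movement.
4. As a sensitivity analysis only, show the HbO result with the within-person speed difference from the foot sensors as covariate. Speed is itself affected by the AFO, so the adjusted estimate should not replace the main one.
5. Regress out short-separation channels only if the device has them.

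The cost is SAP wording and additional analyses, with no new participants or procedures if HbR is available. The downside is precision: HbR has a smaller signal and the interaction is less precise than the main effect, so some HbO findings will be stated more cautiously.

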### AFO Conditions:

1. Walking without an carbon-fiber ankle-foot orthosis (AFO)
2. Walking with a carbon-fiber AFO

### Dual-task conditions

1. Single-task walking
2. Cognitive dual-task walking (auditory Stroop task)
3. Motor dual-task walking (carrying a tray with the non-paretic hand)

During the cognitive dual-task condition, participants will wear a wireless Bluetooth headset and will perform an auditory Stroop task while walking. Participants will be instructed to respond based on the pitch of the auditory stimulus rather than its semantic meaning. For example, when hearing the word “low” presented in a high pitch, participants will respond “high.” All verbal responses will be recorded. Accuracy (correct response rate) and reaction time will be measured. During the motor dual-task condition, participants will be asked to walk while carrying a tray with three wooden blocks stacked on top of each other using their non-paretic hand. The number of blocks that fall from the tray will be recorded. The number of blocks that fall from the tray will be recorded. Each experimental condition will be repeated for five trials, and rest periods will be provided between trials to minimize fatigue.

### **Statistical Analysis Plan:**

Since it is difficult to directly compare the motor and cognitive dual-task walking conditions, the analysis will be conducted separately for each dual-task condition.

To analyze gait parameters, a repeated-measures ANOVA will be used to examine the effects of task condition and AFO use. In addition, dual-task cost (DTC) will also be calculated for each gait parameter to quantify the relative change in performance during dual-task walking. Hotelling’s  $T^2$  test may be used to compare the dual-task cost of multiple gait variables between walking with and without an AFO. To evaluate secondary task performance, Hotelling’s  $T^2$  test will be used to examine the dual-task cost of correct response rate and reaction time between the AFO and no-AFO conditions. To examine changes in oxyhemoglobin(HbO) concentration in the prefrontal cortex, a repeated-measures ANOVA will be conducted at the subject level to test the effects of task and AFO use. If variability in participants’ mobility function is observed, a linear mixed model will be applied to control for accounting for inter individual difference and to evaluate the effects of task and AFO use at the trial level. All statistical analyses will be performed using IBM SPSS Statistics (version 19.0), and the level of statistical significance will be set at  $p < 0.05$ .

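### The default gait and HbO analyses exclude anyone with an empty cell among the four they use, and the mixed model that would keep them depends on an undefined trigger unrelated to missing data

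*Combined protocol and SAP*

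**What the plan says.** The Study Protocol section describes a within-person design with "two AFO conditions (with AFO and without AFO) and three walking task conditions". Under Dual-task conditions, "Each experimental condition will be repeated for five trials, and rest periods will be provided between trials to minimize fatigue". That makes 2 × 3 × 5 = 30 walks per participant.

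The Statistical Analysis Plan then sets out the following:

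- Scope: "the analysis will be conducted separately for each dual-task condition".
- Gait: "To analyze gait parameters, a repeated-measures ANOVA will be used to examine the effects of task condition and AFO use".
- HbO: "a repeated-measures ANOVA will be conducted at the subject level to test the effects of task and AFO use".
- Hotelling's T² is optional for gait dual-task cost ("test may be used to compare the dual-task cost of multiple gait variables between walking with and without an AFO") and planned for the cognitive secondary task ("test will be used to examine the dual-task cost of correct response rate and reaction time between the AFO and no-AFO conditions"). It is not planned for HbO.
- "If variability in participants’ mobility function is observed, a linear mixed model will be applied". This model works at trial level. The sentence follows directly on the HbO sentence and does not mention gait.

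The plan does not say how five walks become one participant value, what happens to an empty cell, or who is in the analysis set.

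**The concern.** Repeated-measures ANOVA, as run in the SPSS procedure for it, needs a complete set of cells for each participant. One empty cell removes that person from the analysis, together with every valid cell they supplied. Paired Hotelling's T² has the same requirement: all the costs being compared must exist under both AFO conditions. Without a missing-data rule, complete-case analysis enters as a software default and not as a choice that anyone has defended.

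Two things are at stake. The first is wasted data, which occurs whenever a cell is empty for any reason. The second is possible bias in the AFO comparison, which arises only under further conditions. There is also a side effect: both dual-task analyses use the same single-task cells, so a participant who is incomplete for one dual task drops out of that analysis only. The single-task AFO contrast may then rest on two different groups of people.

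The mixed model does not settle this. It responds to variability in mobility function, with no threshold, and not to missing cells. Whether it applies to gait is left to the reader.

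**Working it through.** The documents state no non-completion rate, effect size or SD, so there is no figure of the plan's own to reproduce. Everything below is illustration under labelled assumptions.

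**1. Cells per analysis.** The design has 2 × 3 = 6 cells. Reading the separate-analysis rule as single task plus one dual task, each analysis uses 2 × 2 = 4.

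**2. Participants lost.** If each cell is empty independently with assumed probability q, the share excluded is 1 − (1 − q)^k.

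| q | k = 4 | k = 6, for contrast |
|---|---|---|
| 1% | 3.9% | 5.9% |
| 2% | 7.8% | 11.4% |
| 5% | 18.5% | 26.5% |
| 10% | 34.4% | 46.9% |

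For example, 1 − 0.95⁴ = 1 − 0.8145 = 18.5%.

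**3. Missed walks versus empty cells.** If the completed walks are averaged, a cell is empty only when all five walks fail. With a 10% independent chance of missing each walk, the share excluded is 1 − (1 − 0.1⁵)⁴ = 0.004%. Scattered missed walks therefore cost almost nobody, provided that available walks are averaged. Stopping before a cell begins, or losing a whole cell, is what matters.

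**4. When exclusion biases the AFO effect.** Let mobility m have mean 0 and SD 1, and let the AFO effect be 1 + g·m. Among completers the effect is 1 + g × (mean m of completers). With 5% to 20% excluded and a logistic link to mobility of slope 1 to 2, completers average 0.05 to 0.26 SD above the full group.

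- g = −0.5: 1 − 0.5 × 0.047 = 0.98, down to 1 − 0.5 × 0.261 = 0.87.
- g = +0.5: by the same arithmetic, 1.02 up to 1.13.
- g = 0, or no link between mobility and exclusion: 1.00.

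**5. What a mixed model would recover.** The assumptions are comfortable speed 0.60 m/s (SD 0.20), true AFO gain 0.050 (SD 0.05), dual-task slowing 0.08 (SD 0.04), measurement SD 0.03, and 10% or 20% of participants with the no-AFO dual-task cell empty. The simulation used 1,000,000 participants. The entries are the AFO effect averaged over the two tasks, in m/s, at 10% / 20% missing.

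| Gain–speed correlation | A: complete cases | A: mixed model | B: complete cases | B: mixed model |
|---|---|---|---|---|
| −0.5 | 0.047 / 0.044 | 0.050 / 0.050 | 0.045 / 0.041 | 0.049 / 0.047 |
| −0.3 | 0.048 / 0.046 | 0.050 / 0.050 | 0.047 / 0.044 | 0.049 / 0.047 |
| 0 | 0.050 / 0.050 | 0.050 / 0.050 | 0.050 / 0.049 | 0.049 / 0.047 |
| +0.3 | 0.052 / 0.053 | 0.050 / 0.050 | 0.052 / 0.054 | 0.049 / 0.047 |

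In A, loss depends on the observed no-AFO single-task speed (logistic, slope 1.5 per SD). In B, the cell is lost when its own value is in the lowest 10% or 20%. The mixed model is the unstructured likelihood estimate.

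**6. Covariance structure.** With complete data, the unstructured model estimates each AFO or task contrast with its own variance. In a 2 × 2 layout this gives the same F as the ANOVA. Compound symmetry pools the error terms. In one complete simulated data set with n = 20, the AFO test was F(1,19) = 10.2 by ANOVA and F(1,57) = 16.8 under compound symmetry.

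**The case against.** The best defence is that little may be lost. The walks are 13 m at comfortable speed with rests between trials, there are five per cell, and nothing in the plan forbids averaging those completed; step 3 shows how few participants would then drop out. The separate-analysis rule also protects a participant who misses only the tray task, who stays in the cognitive analysis. The trial-level mixed model would keep incomplete participants if it were applied, and its sentence is not expressly confined to HbO.

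Much of this stands, and it limits the point. It does not remove it: averaging is not stated, empty cells are not covered, and the mixed model hangs on a condition that someone must judge after seeing data.

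A reader might go further and infer that the plan removes the weakest walkers and so understates the AFO benefit. The documents do not support that. They report no stopping rates or reasons, do not say that participants were recruited for foot drop (the background only calls it common after stroke), and do not say who benefits most. The direction follows from an assumed negative link between gain and speed: the complete-case estimate is almost unbiased at zero correlation and too high at +0.3. Nor must all six cells be complete, and Hotelling's T² does not touch HbO.

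It is also fair to object that a mixed model is no cure when stopping depends on the unseen walk itself. Column B shows partial recovery with a negative correlation and a slightly worse result than complete cases at zero.

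**Conclusion.** The point holds in a limited form and should be dealt with before analysis. The default gait and HbO analyses are complete-case within each four-cell analysis, and so are the Hotelling tests on secondary-task cost and, if used, gait cost. No missing-data rule is given, and the model that would help is conditional on something else.

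The loss of data is certain wherever cells are empty. Its size is unknown: 3.9% to 34.4% of participants per analysis for assumed independent empty-cell rates of 1% to 10%, and close to none if only scattered walks are missed and the rest are averaged.

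Bias is conditional. Apart from a small residue from selection on measurement noise, it needs non-completion and AFO benefit both to vary with walking ability, and its sign follows the sign of that second link. In scenario A with correlations of −0.3 to −0.5, complete cases gave 0.044 to 0.048 against a true 0.050, a shortfall of 4% to 12%, and the unstructured model returned 0.050. These figures rest on assumed inputs and predict nothing about this trial.

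**What to change.** For each dual-task analysis, name a likelihood-based linear mixed model (SPSS MIXED) as the primary analysis of gait parameters and HbO.

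- **Data:** all available participant-by-condition means, each being the mean of the valid walks completed. Participants with some empty cells stay in.
- **Model:** AFO, task and AFO × task as fixed effects, with an unstructured within-participant covariance. Compound symmetry should not be offered as an alternative, for the reason in step 6.
- **Trigger:** delete the condition about observed variability in mobility function.
- **Reporting:** give incomplete walks and empty cells by AFO condition and task.
- **Sensitivity:** report the complete-case repeated-measures ANOVA alongside.

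The cost is SAP wording and slightly more analysis work, in software already named. An unstructured matrix for four cells has 4 × 5 / 2 = 10 covariance parameters against 2 for compound symmetry, which is more to estimate. The model assumes data missing at random given what was observed. It may therefore reduce bias without removing it if stopping depends on the walk that was not recorded, which is why the counts and the sensitivity analysis belong in the report.

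### The plan tests the dual-task cost of Stroop accuracy and reaction time but describes no Stroop-only condition, so neither cost can be calculated as written.

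*Combined protocol and SAP*

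**What the plan says.** The Design paragraph of the Study Protocol crosses two AFO conditions with "three walking task conditions (single-task walking, cognitive dual-task walking, and motor dual-task walking". The Dual-task conditions section lists the same three tasks. The only one labelled single-task is "Single-task walking".

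For the cognitive condition, that section says participants "will perform an auditory Stroop task while walking", and then "Accuracy (correct response rate) and reaction time will be measured". The Stroop task is not described in any other setting.

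The Statistical Analysis Plan introduces dual-task cost for gait: "dual-task cost (DTC) will also be calculated for each gait parameter to quantify the relative change in performance during dual-task walking". It gives no formula. It then applies the same term to the secondary task, committing to Hotelling's T² to "examine the dual-task cost of correct response rate and reaction time between the AFO and no-AFO conditions". It does not say whether the paired form of the test is meant.

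**The concern.** Dual-task cost expresses how far a measure changes when a second task is added, so it needs that measure's value when the task is done alone. For gait, single-task walking provides this. For the Stroop task nothing described in the plan does, because walking alone produces no responses to score or time.

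The stated aim includes the effect of the AFO on dual-task performance, and Stroop performance is one side of that in the cognitive condition. The sentence at issue is the only planned analysis of secondary-task performance: falling blocks are to be counted in the tray condition, but the SAP names no test for them. If the sentence cannot be carried out, the analyst must choose a replacement, possibly after seeing the data. A missing reference also cannot be recovered once the visits are over.

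**Working it through.** There is no sample size or other stated figure to reproduce. The check is whether each planned cost has both of its terms.

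**Inputs.** From the Study Protocol (Design): 2 AFO conditions and 3 walking tasks. From Dual-task conditions: the Stroop task is done while walking, and its measures are correct response rate and reaction time. From the SAP: cost is a relative change. The formula is my assumption, as the SAP gives none: cost = (dual − single) / single, with the sign reversed where a fall in the measure is the cost.

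**Step 1: count the cells.** 2 × 3 = 6 cells, all walking.

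| Measure | Dual-task value in the cognitive condition | Single-task value |
|---|---|---|
| Gait parameters | yes, with and without AFO | yes, single-task walking with and without AFO |
| Stroop correct response rate | yes, with and without AFO | none described |
| Stroop reaction time | yes, with and without AFO | none described |

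Stroop data exist in 2 of 6 cells, and there are 0 Stroop-only cells. So 2 of the 2 planned Stroop cost variables lack the single-task term.

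**Step 2: does the missing term matter to the value?** Assume dual-task reaction times of 1000 ms without the AFO and 950 ms with it, and let the unmeasured Stroop-only time vary:

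| Assumed Stroop-only time (ms) | Cost without AFO | Cost with AFO |
|---|---|---|
| 700 | 300/700 = 42.9% | 250/700 = 35.7% |
| 800 | 200/800 = 25.0% | 150/800 = 18.8% |
| 900 | 100/900 = 11.1% | 50/900 = 5.6% |
| 1000 | 0/1000 = 0.0% | −50/1000 = −5.0% |

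The same observed data fit a large cost or none, so the data to be collected do not determine it.

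**Step 3: what do the raw values give instead?** Let b be one participant's Stroop-only value, used for both AFO conditions, and x the dual-task value.

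- Absolute cost: (x_AFO − b) − (x_noAFO − b) = x_AFO − x_noAFO. The baseline cancels.
- Relative cost: (x_AFO − b)/b − (x_noAFO − b)/b = (x_AFO − x_noAFO)/b. The raw difference is divided by that participant's own b.

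Within a participant, then, the baseline only rescales the difference. Across participants, relative cost weights each difference by 1/b.

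As an illustration, I used one simulated data set with n = 20 and p = 2 measures. Assumed means (SD) were: Stroop-only accuracy 0.95 (0.02) and time 800 (120) ms; change without AFO −0.08 (0.04) and +150 (60) ms; change with AFO −0.06 (0.04) and +110 (60) ms. The paired statistic is T² = n·d̄′S⁻¹d̄, with F = (n − p)/(p(n − 1)) · T² = (18/38) · T².

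- Raw differences: T² = 10.53, F = 4.99, P = 0.019.
- Absolute cost, common baseline: T² = 10.53, identical.
- Relative cost, common baseline: T² = 10.25, F = 4.85, P = 0.021.

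The raw and relative tests are similar here, but that is not guaranteed. Take two participants with assumed raw differences of +100 ms (b = 1200) and −60 ms (b = 500). The raw mean is (100 − 60)/2 = +20 ms. The relative mean is (8.3% − 12.0%)/2 = −1.8%, which has the opposite sign.

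**The case against.** The strongest reply is that little is lost. Accuracy and reaction time are recorded with and without the AFO, the gait and HbO analyses do not use Stroop cost, and the remedy can be a single sentence. The authors may even have used the word cost loosely for performance during dual-task walking. All of this limits the consequence. It does not rescue the sentence, which names variables that the described data cannot supply and uses a term that the same section has just described as a relative change.

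Three stronger readings are tempting, and the documents do not support them.

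- *A reader might infer that no Stroop-only block will be run.* The document is brief and part of it was not available for review. What can be said is that none is described, although the design, conditions and analysis sections are all present. If a block is intended, it needs to be written in.
- *A reader might infer that a baseline would be useless for the AFO comparison.* That is exact for absolute cost with one common baseline per participant. It fails for relative cost when baselines differ between participants, as Step 3 shows. It would also fail if a standing Stroop were done both with and without the AFO, giving two baselines. The plan does not say which kind of reference was meant.
- *A reader might infer that better gait or lower HbO with the AFO could not be told apart from reduced effort on the Stroop task.* The raw measures needed to look for this are collected in both AFO conditions. What is missing is a prespecified analysis of them that can be run.

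**Conclusion.** The point holds in a limited form. The planned Hotelling's T² on Stroop dual-task cost lacks its single-task reference for 2 of 2 variables and cannot be run as written. It is the only planned analysis of secondary-task performance, which belongs to the stated aim, so it should be corrected before analysis.

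The defect does not extend to gait dual-task cost or to the repeated-measures ANOVAs, and it destroys no data. The conclusion rests on two things: that the conditions described are the full set, and that cost carries its usual meaning of change from a single-task value of the same measure, in line with the SAP's own description for gait. The reaction times and simulated values above are assumptions for illustration and do not bear on the conclusion.

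**What to change.** In the Statistical Analysis Plan, replace the Stroop cost analysis with a paired (within-participant) Hotelling's T² on raw correct response rate and raw reaction time during cognitive dual-task walking, AFO versus no AFO, followed by the two paired contrasts. This uses data already planned and costs one sentence.

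The small downside is that it does not show how much walking itself degrades Stroop performance. If that is wanted, add a short Stroop-only block to the protocol before data collection, at a cost of a few minutes per participant. State whether it is seated or standing, and whether one reference serves both AFO conditions. Give the cost formula for each measure, absolute or relative, since the two can give different tests.
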